9.5 Statistical Methods

9.5.1 Statistical Methods for Safety Analyses

Safety will be summarized separately for the oral run-in doses of MK-8189 [Period 1] and IM single-ascending doses of MK-5720 [Period 2]. The following will be done for both periods.

Incidence of AEs will be descriptively summarized. Summary statistics and plots will be generated for raw laboratory safety tests, ECGs, and VS as well as for change from baseline, as deemed clinically appropriate. Depending on the safety parameter, the difference from baseline will either be computed on the original scale (raw change from baseline) or on the log scale and back-transformed for reporting (percent change from baseline).

Summary statistics and plots will be generated for BARS, AIMS, SAS, and BPRS, as well as for change from baseline. Responses to the C-SSRS will be listed.

9.5.2 Statistical Methods for Pharmacokinetic Analyses

The following analyses are for Period 1 of the protocol (oral run-in doses of MK-8189).

Individual values will be listed for each PK parameter, and the following (non-model-based) descriptive statistics will be provided: N (number of participants with non-missing data), arithmetic mean, standard deviation, arithmetic percent coefficient of variation (CV, calculated as $100 \times \text{standard deviation}/\text{arithmetic mean}$), median, minimum, maximum, geometric mean, and geometric percent CV (calculated as $100 \times \text{sqrt}(\exp(s2) - 1)$, where $s2$ is the observed variance on the natural log-scale).

[figure not shown]
The following analyses are for Period 2 of the protocol (IM single-ascending doses of MK-5720).

Model-based PK summary

Separately for each PK parameter, individual values of plasma MK-5720 (AUC0-last, AUC-inf, and Cmax) and plasma MK-8189 (AUC0-28d, AUC0-inf, Cmax, and C28d), after administration of a single dose of MK-5720 from Panels A through F will be natural log-transformed and evaluated with a linear effects model containing a fixed effect for treatment. Kenward and Roger's method will be used to calculate the denominator degrees of freedom for the fixed effects. Ninety-five percent CIs for the least squares means for each treatment will be constructed on the natural log scale and will reference a t-distribution. Exponentiating the least-squares means and lower and upper limits of these CIs will yield estimates for the population GMs and CIs about the GMs on the original scale. A sample code is as follows:

```
proc mixed data=adpp;
  class treatment;
  model lnpk=treatment/ddfm=kr;
  lsmeans treatment/alpha=0.05 cl;
  run;
```

CCI

PK Comparison of Deltoid vs Gluteal Muscle

A comparison between Deltoid and Gluteal Muscle will be evaluated using the above linear model at a common dose level for plasma MK-5720 and plasma MK-8189. If appropriate, dose normalization prior to construct of comparison and subsequent calculation of the geometric mean ratios and corresponding 90% confidence interval will be implemented.

Descriptive Statistics

Individual values will be listed for each PK parameter by treatment (for MK-5720 and MK-8189), and the following (non-model-based) descriptive statistics will be provided: N (number of participants with non-missing data), arithmetic mean, standard deviation, arithmetic percent coefficient of variation (CV, calculated as $100 \times \text{standard deviation}/\text{arithmetic mean}$), median, minimum, maximum, geometric mean, and geometric percent CV (calculated as $100 \times \text{sqrt}(\exp(s2) - 1)$, where s2 is the observed variance on the natural log-scale).

QTc Analysis

QTc will be evaluated through development of a model describing the relationship between QTc change from baseline and MK-5720 plasma concentrations and the relationship between QTc change from baseline and MK-8189 plasma concentrations. Details of the concentration-QTc analysis will be specified in a separate modeling analysis plan (MAP). This MAP will be completed prior to unblinding and database lock. The planned analysis will be aligned with the Scientific White Paper on Concentration-QTc modeling - A Review [Garnett, C., et al 2017]. Results of this analysis will be reported separately from the CSR.

Counts will be provided by dose and time point for QTc values falling in the following ranges: ≤ 450 , > 450 , > 480 and > 500 msec. Counts will also be provided by dose and time point for QTc change from baseline values falling in the following ranges: < 30 , ≥ 30 and ≥ 60 msec. Means and 90% confidence intervals for QTc and QTc change from baseline will be provided for each dose.

Exploratory Analysis

The depot volume and surface area from the MRI images will be summarized using descriptive statistics including mean, standard deviation, median, minimum, and maximum, by deltoid muscle and gluteal muscle.

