- d. Day 1 Safety Assessments
 1. Predose: VS assessments (HR and BP) and ECG will be completed in triplicate (postdose assessments will be single measurements), RR and orthostatic VS (HR and BP) will be single measurements.
 2. Up to 24 hours: VS assessments (including orthostatic VS) (HR, BP, RR) will be collected at 2-, 6-, and 12-hour postdose in single measurements.
- e. Temperature will be assessed at Screening and Predose Day 1 only and will require single measurements.
- f. Vitals and ECG on Days 2, 4 will be taken only for Panel E and F if the daily MK-8189 oral dose exceeds 24 mg corresponding to MK-5720 dose greater than 280 mg..
- g. The assessment can be done at any time during the day however an attempt should be made for consistent timing across days and periods.
- h. Hematology, chemistry, urinalysis can be use for predose labs in Period 2 as long as they are obtained 24 hours prior to dosing MK-5720.
- i. Additional BARS, AIMS, and SAS assessments should be conducted, as soon as reasonably possible, when there are observed or reported complaints of dystonia and/or akathisia
- j. PK Timepoints for MK-8189
 1. Day 1: predose, 2, 6, 8, 10, 12, and 16 hours postdose
 2. Day 2: 24-hour postdose relative to D1 dose administration
 3. Day 7: predose, 2, 6, 8, 10, 12, 16 hours postdose
 4. Day 8: 24 hours postdose for D7 dose administration
 5. Day 9: 48 hours postdose for D7dose administration
 6. Day 10: 72 hours postdose for D7 dose administration
- k. This sample should be drawn for planned analysis of the association between genetic variants in DNA and drug response. This sample will not be collected at that site if there is either a local law or regulation prohibiting collection, or if the IRB/IEC does not approve the collection of the sample for these purposes. If the sample is collected, leftover extracted DNA will be stored for FBR if the participant (or their legally acceptable representative) provides documented informed consent for FBR. If the planned genetic analyses are not approved, but FBR is approved and consent is given, this sample will be collected for the purpose of FBR.

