MK-5720-001 clinical study will consist of 6 panels (A, B, C, D, E, and F) and two treatment periods, Periods 1 and 2. Period 1 will include an oral tolerability run-in period with participants receiving once-daily administration of MK-8189 (or corresponding placebo) for 7 days followed by a washout period of at least 72 hours prior to initiation of Period 2. Participants will receive rising single dose IM injection of MK-5720 (or corresponding placebo) in Period 2. The dose of MK-8189 (or placebo) used in Period 1 will vary based on each panel as mentioned in [\[Table 1\]](#). Approximately 8 participants (n=6 for MK-8189/MK-5720 and n=2 for placebo) will be in Panels A and B and approximately 12 participants (n=9 for MK-8189/MK-5720 and n=3 for placebo) in Panels C through F. Each panel will sequentially receive single rising IM doses of MK-5720 and the corresponding dose of oral MK-8189 as mentioned in [Table 1](#). Each participant will be assigned to 1 of 6 panels and will participate in both treatment periods. Participants will be randomized to receive a single IM injection of MK-5720 or placebo and oral MK-8189 or placebo in a blinded fashion. Panels A through C will investigate IM doses of MK-5720 in the deltoid muscle while Panels D through F will investigate IM doses in the deltoid or gluteal muscle based on PK data obtained from Panels A to C. Since patient preference for injection sites differ between geographic regions, the effect of the site of administration of MK-5720 LAI on plasma PK of MK-5720 and MK-8189 following a single dose of MK-5720 LAI administered IM in the gluteal muscle relative to administration in the deltoid muscle will be compared. Currently, the literature on this topic is sparse, but the published data show discrepancies in the elimination half-life, peak plasma concentration, and absorption rate that are dependent on the site of injection. Hence, both PK and safety of MK-5720 LAI will be compared between both IM sites of administration at the highest well tolerated dose of MK-5720 to potentially offer the choice of administration into either the deltoid or gluteal muscle to meet patient and physician preference in future clinical studies. MK-5720 LAI will be administered as a suspension for injection for doses up to ≤ 560 mg that will be administered IM using the appropriate needle size/gauge based on the participant's BMI and site of LAI administration.

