8.1.8 Study Intervention Administration

Period 1

Study intervention(s) will be administered by the investigator and/or study staff. Participants will fast from all food and drinks, except water, for at least 8 hours prior to study drug administration each day. Approximately 240 mL of water will be provided during study drug administration but will be restricted 1 hour prior to and 1 hour after study drug administration. Details on water and dietary restrictions are outlined in Section 5.3.1. Site staff will ensure that participants have swallowed study treatment.

Period 2

Study intervention(s) will be administered by the investigator and/or an appropriately qualified designee according to the specifications within the pharmacy manual.

In Panels A to C, participants will receive an IM injection in the deltoid. For Panels D to F, participants will receive an IM injection in the deltoid or in their gluteal muscle as directed by the Sponsor.

Study intervention and placebo will be provided to the study staff will require reconstitution by site staff according to the directions in the Method of Preparation. Study intervention(s) will be provided to the study staff in prefilled syringes from the pharmacy. Syringes will be covered with a blinding label. However, there is a significant visual difference between the active and placebo formulations, the unit staff who are involved in study drug administration cannot be involved in other areas of study conduct to maintain blinding. Site staff should use the appropriate needle length and gauge for administering study intervention based on the BMI of the participants.

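### The deltoid-gluteal comparison is non-randomised and its only readable model term is treatment; a covariate-adjusted version using each participant's Day 7 oral MK-8189 exposure would be a cheap addition

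*Combined protocol and SAP*

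**What the plan says.** The site comparison is a secondary objective (Section 3). Section 4.1 gives its purpose: to allow a choice of muscle in future studies. Section 9.5.2 plans it as follows: "A comparison between Deltoid and Gluteal Muscle will be evaluated using the above linear model at a common dose level". The model referred to is "evaluated with a linear effects model containing a fixed effect for treatment", and the sample code reads "model lnpk=treatment/ddfm=kr". The output is "geometric mean ratios and corresponding 90% confidence interval", with an option: "If appropriate, dose normalization prior to construct of comparison". No margin or test is readable.

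On how site is set, Section 4.1 says "Panels D through F will investigate IM doses in the deltoid or gluteal muscle based on PK data obtained from Panels A to C", and Section 8.1.8 says "For Panels D to F, participants will receive an IM injection in the deltoid or in their gluteal muscle as directed by the Sponsor". Panels are dosed in sequence. The randomisation in Table 1 and Section 6.3.1 is to active or placebo within a panel, and Section 6.3.2 uses no stratification.

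In Period 1, before the injection, Section 1.3.1 schedules oral MK-8189 sampling on "Day 7: predose, 2, 6, 8, 10, 12, 16 hours postdose", then at 24, 48 and 72 hours. Section 4.2.1.3 derives AUC0-24 on Days 1 and 7. Section 9.5.2 lists and summarises these values, and no readable text connects them to the Period 2 model.

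**The concern.** With one panel per site, injection site and panel are the same variable in the analysis. A systematic difference in MK-8189 clearance between the two groups, for example from a change in who is recruited over time, would then appear in the site ratio.

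The trial already measures something that speaks to this. MK-5720 is hydrolysed to MK-8189 (Section 2.1), so oral and post-injection MK-8189 exposure share systemic clearance. The oral measurement precedes the injection, so site cannot affect it and it is a valid baseline covariate. At stake are the width of the interval on a secondary objective and some protection against one source of confounding.

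**Working it through.** **Inputs from the documents.** Panels A and B have 6 active and 2 placebo participants each; Panels C to F have 9 and 3 (Table 1). Total: 2×(6+2) + 4×(9+3) = 64, which matches the Synopsis. Active: 2×6 + 4×9 = 48.

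**Assumed inputs.** The documents give no readable between-participant SD for Period 2 and no correlation (rho) between log oral AUC and the log post-injection parameter. I take CV 40%, with 30% and 60% as a range, and rho 0.3, 0.5 and 0.7. I take one panel per site at a common dose, 9 vs 9, with each panel its own treatment level, giving 48 − 6 = 42 residual degrees of freedom.

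**Unadjusted interval.**
- Log SD: s = sqrt(ln(1 + 0.40²)) = 0.385.
- SE of the log ratio: 0.385 × sqrt(2/9) = 0.182.
- Half-width: t(0.95, 42) × SE = 1.682 × 0.182 = 0.306.
- 90% CI factors around the ratio: exp(±0.306) = 0.74 to 1.36.

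**Adjusted interval.** Multiply the SE by sqrt(1 − rho²) and by sqrt(1 + 1/41) for estimating the slope, and use 41 df. For two panels alone, df go from 16 to 15 and the slope factor is sqrt(1 + 1/14). (The expected pooled factor is strictly 1 + 1/40; this changes nothing at the precision shown.)

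| CV 40% | pooled, six panels | two panels only |
|---|---|---|
| unadjusted | 0.74-1.36 | 0.73-1.37 |
| rho 0.3 | 0.74-1.34 | 0.73-1.37 |
| rho 0.5 | 0.765-1.31 | 0.75-1.33 |
| rho 0.7 | 0.80-1.25 | 0.79-1.27 |

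At CV 30% the pooled factors go from 0.79-1.26 unadjusted to 0.85-1.18 at rho 0.7; at CV 60%, from 0.64-1.55 to 0.73-1.37.

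**Break-even.** Adjustment lowers the variance only if (1 − rho²)(1 + 1/41) < 1, that is rho above about 0.15 pooled. With 1 + 1/14 the threshold is about 0.26.

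**Systematic shift (hypothetical).** If one panel's log oral exposure is shifted by d SD, the unadjusted ratio is multiplied by exp(rho × s × d). For d = 0.5 and rho 0.3, 0.5 and 0.7: exp(0.058) = 1.06, exp(0.096) = 1.10 and exp(0.135) = 1.14. Adjustment returns it to about 1.00.

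**Chance imbalance only.** In a six-panel simulation (CV 40%, true ratio 1, 4,000 runs per setting) with no systematic shift, the unadjusted 90% interval covered the truth in 89% to 90% of runs at every rho from 0 to 0.7. With a 0.5 SD shift at rho 0.7, unadjusted coverage fell to 81% and adjusted coverage was 90%.

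**The case against.** The strongest reply is that the planned interval is valid as it stands unless panels differ systematically. A reader might infer that a chance clearance difference between two small panels biases the ratio. It does not: that variation is already in the residual SD and so in the interval, as the coverage above shows. Removing it is the same gain as the narrower interval and must not be counted twice. Nor do the documents show a systematic shift: eligibility and the CYP3A restrictions apply to all panels, apart from the two MRI exclusions, which apply only to imaging panels. This part of the objection stands, and it limits the bias argument to insurance.

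The correlation is also unsupported. The projected half-life from the depot is about 10 days (Section 4.2), against 8-9 hours orally (Section 4.3), so depot release should drive much of Cmax and C28d. Oral AUC also carries oral bioavailability, which an injection does not share. Rho may therefore be low, especially for those two parameters. This stands too.

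The adjustment can add error. Oral run-in doses differ by panel and may be lowered (Table 1). If the compared panels took different oral doses, dose-normalising the covariate assumes proportional oral PK, which the readable text does not establish.

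A reader might also infer that the plan certainly omits any covariate, that 9 vs 9 is fixed, or that every active participant will have a Day 7 AUC. The documents do not support any of these. Text is blacked out between the sample code and the site comparison; Sections 4.1 and 8.1.8 do not fix one panel per site; and Section 8.6 lets the Sponsor decide which samples are assayed.

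What survives is that no random assignment to site is described, and a pre-injection measure tied to MK-8189 clearance is collected without any readable use in this comparison.

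**Conclusion.** The point holds as a cheap improvement, at the level of consider. The planned comparison is a non-randomised, between-panel estimate whose only readable model term is treatment. Adjusting for Day 7 oral exposure would probably help the MK-8189 AUC parameters, by an amount the documents do not allow anyone to fix: almost nothing at rho 0.3 when two panels are fitted, and a narrowing from 0.74-1.36 to about 0.80-1.25 at rho 0.7 with pooled panels. Both figures assume CV 40% and 9 vs 9.

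It would also protect against a systematic panel difference in oral exposure, should one occur. It would not make the comparison equivalent to a randomised one: differences in BMI, needle, clinic and depot behaviour would remain. Nor can a site effect be called wholly indistinguishable from a clearance difference under the current plan, because the listed Period 1 values would let a reader see a marked imbalance. The argument does not extend to MK-5720, whose conversion is by esterases.

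**What to change.** Before unblinding, add to the SAP:

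- For plasma MK-8189 AUC0-28d and AUC0-inf, and with less expected gain Cmax and C28d, a second version of the site-comparison model with log Day 7 oral AUC0-24 as covariate, reported alongside the planned unadjusted model.
- The covariate is not centred within panel, since centring would leave any between-panel difference in the ratio.
- Dose-normalise the covariate only if the oral doses of the compared panels differ, and then state the proportionality assumption.
- MK-5720 parameters stay unadjusted.
- A commitment to assay the Day 7 samples of active participants in every panel used to fit the adjusted model.
- A statement, carried into the CSR, that the comparison is non-randomised and that BMI, needle, clinic and depot differences are not addressed.

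The cost is SAP wording and one degree of freedom (42 to 41 pooled, or 16 to 15 with two panels). Precision falls slightly if rho is below about 0.15 pooled or 0.26 with two panels. Participants without a Day 7 AUC are lost from the adjusted model only. No new sample, visit or participant is needed.

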9.6 Interim Analyses

During the in-life portion of the trial, descriptive summary level results (PK, biomarkers, and/or safety (labs, VS, ECGs)) will be prepared as needed to support decision-making meetings such as dose escalation meetings. The aggregate summaries will be presented in an unblinded manner. No individual participant level results will be provided. There are no planned interim analyses to test any formal hypotheses.

[figure not shown]
9.7 Multiplicity

The hypothesis related to target PK will be addressed using posterior probabilities, therefore, there is no need for a multiplicity adjustment.

9.8 Sample Size and Power Calculations

The following power applies to Period 2 of the protocol (IM single-ascending doses of MK-5720).

CCI

10 SUPPORTING DOCUMENTATION AND OPERATIONAL CONSIDERATIONS

10.1 Appendix 1: Regulatory, Ethical, and Study Oversight Considerations

10.1.1 Code of Conduct for Interventional Clinical Trials

Merck Sharp & Dohme LLC, Rahway, NJ, USA (MSD)

I. Introduction

A. Purpose

Merck Sharp & Dohme LLC, Rahway, NJ, USA (MSD), through its subsidiaries, conducts clinical trials worldwide to evaluate the safety and effectiveness of our products. As such, we are committed to designing, planning, conducting, analyzing, and reporting these trials in compliance with the highest ethical and scientific standards. Protection of participants in clinical trials is the overriding concern in the design and conduct of clinical trials. In all cases, MSD clinical trials will be conducted in compliance with MSD's global standards, local and/or national regulations (including all applicable data protection laws and regulations), and International Council for Harmonisation Good Clinical Practice (ICH GCP) E6 and ICH General Considerations for Clinical Studies E8, and in accordance with the ethical principles that have their origin in the Declaration of Helsinki.

B. Scope

Highest ethical and scientific standards shall be endorsed for all clinical interventional investigations sponsored by MSD irrespective of the party (parties) employed for their execution (e.g., contract research organizations, collaborative research efforts). This Code is not intended to apply to trials that are observational in nature, or which are retrospective. Further, this Code does not apply to investigator-initiated trials, which are not under the full control of MSD.

II. Scientific Issues

A. Trial Conduct

1. Trial Design

Except for pilot or estimation trials, clinical trial protocols will be hypothesis-driven to assess safety, efficacy, and/or pharmacokinetic or pharmacodynamic indices of MSD or comparator products. Alternatively, MSD may conduct outcomes research trials, trials to assess or validate various endpoint measures, or trials to determine patient preferences, etc.

The design (i.e., participant population, duration, statistical power) must be adequate to address the specific purpose of the trial and shall respect the data protection rights of all participants, trial site staff and, where applicable, third parties. Input may be considered from a broad range of stakeholders, including patient advocacy groups/patients representing the trial population, caregivers, and healthcare providers to ensure operational feasibility. Trial design also

includes proactive identification of critical to quality factors utilizing a risk-based approach. Plans are then developed to assess and mitigate risks to those factors as appropriate during the trial. All trial protocols are and will be assessed for the need and capability to enroll underrepresented groups. Participants must meet protocol entry criteria to be enrolled in the trial.

2. Site Selection

MSD's clinical trials are conducted globally in many different countries and in diverse populations, including people of varying age, race, ethnicity, gender, and accounting for other potential disease related factors. MSD selects investigative sites based on medical expertise, access to appropriate participants, adequacy of facilities and staff, previous performance in clinical trials, as well as budgetary considerations. Prior to trial initiation, sites are evaluated by MSD personnel (or individuals acting on behalf of MSD) to assess the ability to successfully conduct the trial. Individuals involved in trial conduct receive training commensurate with their role prior to their becoming involved in the trial.

Where appropriate, and in accordance with regulatory authority guidance, MSD will make concerted efforts to raise awareness of clinical trial opportunities in various communities. MSD will seek to engage underrepresented groups and those disproportionately impacted by the disease under study. MSD will support clinical trial investigators to enroll underrepresented groups and expand access to those who will ultimately use the products under investigation.

3. Site Monitoring/Scientific Integrity

Investigative trial sites are monitored to assess compliance with the trial protocol and Good Clinical Practice (GCP). MSD reviews clinical data for accuracy, completeness, and consistency. Data are verified versus source documentation according to standard operating procedures. Per MSD policies and procedures, if potential fraud, scientific/research misconduct, privacy incidents/breaches or Clinical Trial-related Significant Quality Issues are reported, such matters are investigated. When necessary, appropriate corrective and/or preventative actions are defined and regulatory authorities and/or ethics review committees are notified.

B. Publication and Authorship

Regardless of trial outcome, MSD commits to publish the primary and secondary results of its registered trials of marketed products in which treatment is assigned, according to the pre-specified plans for data analysis. To the extent scientifically appropriate, MSD seeks to publish the results of other analyses it conducts that are important to patients, physicians, and payers. Some early phase or pilot trials are intended to be hypothesis generating rather than hypothesis testing; in such cases, publication of results may not be appropriate since the trial may be underpowered and the analyses complicated by statistical issues such as multiplicity.

MSD's policy on authorship is consistent with the recommendations published by the International Committee of Medical Journal Editors (ICMJE). In summary, authorship should reflect significant contribution to the design and conduct of the trial, performance or interpretation of the analysis, and/or writing of the manuscript. All named authors must be able to defend the trial results and conclusions. MSD funding of a trial will be acknowledged in publications.

III. Participant Protection

A. Regulatory Authority and Ethics Committee Review (Institutional Review Board [IRB]/Independent Ethics Committee [IEC])

All protocols and protocol amendments will be submitted by MSD for regulatory authority acceptance/authorization prior to implementation of the trial or amendment, in compliance with local and/or national regulations.

The protocol, protocol amendment(s), informed consent form, investigator's brochure, and other relevant trial documents must be reviewed and approved by an IRB/IEC before being implemented at each site, in compliance with local and/or national regulations and ICH Guidelines. Changes to the protocol that are required urgently to eliminate an immediate hazard and to protect participant safety may be enacted in anticipation of ethics committee approval. MSD will inform regulatory authorities of such new measures to protect participant safety, in compliance with local and/or national regulations.

B. Safety

The guiding principle in decision-making in clinical trials is that participant welfare is of primary importance. Potential participants will be informed of the risks and benefits of, as well as alternatives to, trial participation. At a minimum, trial designs will take into account the local standard of care.

All participation in MSD clinical trials is voluntary. Participants enter the trial only after informed consent is obtained. Trial designs include procedures and systems for the identification, monitoring, and reporting of safety concerns. Participants may withdraw from an MSD trial at any time, without any influence on their access to, or receipt of, medical care that may otherwise be available to them.

During trial planning, the need for an independent Data Monitoring Committee (DMC) is assessed. DMC review of data accumulated during the conduct of the trial is integral to the well-being of trial participants.

C. Confidentiality

MSD is committed to safeguarding participant confidentiality, to the greatest extent possible, as well as all applicable data protection rights. Unless required by law, only the investigator, Sponsor (or individuals acting on behalf of MSD), ethics committee, and/or regulatory authorities will have access to confidential medical records that might identify the participant by name.

D. Genomic Research

Genomic research will only be conducted in accordance with a protocol and informed consent authorized by an ethics committee.

E. Trial Results

At the time of providing informed consent and in accordance with local laws and regulations, participants should be informed about the plans for availability of trial results.

IV. Financial Considerations

A. Payments to Investigators

Clinical trials are time- and labor-intensive. It is MSD's policy to compensate investigators (or the sponsoring institution) in a fair manner for the work performed in support of MSD trials. MSD does not pay incentives to enroll participants in its trials. However, when enrollment is particularly challenging, additional payments may be made to compensate for the time spent in extra recruiting efforts.

MSD does not pay for participant referrals. However, MSD may compensate referring physicians for time spent on medical record review and medical evaluation to identify potentially eligible participants.

B. Clinical Research Funding

Informed consent forms will disclose that the trial is sponsored by MSD, and that the investigator or sponsoring institution is being paid or provided a grant for performing the trial. However, the local ethics committee may wish to alter the wording of the disclosure statement to be consistent with financial practices at that institution. As noted above, all publications resulting from MSD trials will indicate MSD as a source of funding.

C. Funding for Travel and Other Requests

Funding of travel by investigators and support staff (e.g., to scientific meetings, investigator meetings, etc) will be consistent with local guidelines and practices.

V. Investigator Commitment

Investigators will be expected to review MSD's Code of Conduct as an appendix to the trial protocol, and in signing the protocol, agree to support these ethical and scientific standards.

